#### **Time to Progression**

Time to progression will be calculated as the time from start of treatment until PD (as determined by the site investigator based on the mIMWG criteria). Subjects not experiencing a documented progression will be censored at the time of their last response assessment (or at the time of trial enrollment if no assessment was conducted).

#### **Progression-free Survival**

Progression-free survival will be calculated as the time from start of treatment until the time of PD (as determined by the site investigator based on the mIMWG criteria) or death from any cause on study treatment, whichever comes first. Subjects not experiencing a documented progression will be censored at the time of their last response assessment (or at the time of trial enrollment if no assessment was conducted).

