### **Overview of Efficacy Assessments**

Tumor response, will be based on investigator's assessment using local imaging review (if applicable) and central laboratory results according to modified International Myeloma Working Group (mIMWG) criteria (per [Appendix B](#)).

For subjects with daratumumab interference on serum immunofixation (IFE), the SEBIA Hydrashift 2/4 Daratumumab IFE Interference test will be used to distinguish a positive SPEP/IFE due to the presence of daratumumab versus the presence of underlying (endogenous) monoclonal protein. Subjects that meet all other International Myeloma Working Group (IMWG) criteria for complete response (CR), and whose positive IFE is confirmed to be daratumumab, will be considered complete responders.

For subjects with light chain multiple myeloma, both serum and urine immunofixation test and serum free light chain assay will be performed routinely. As daratumumab is a monoclonal IgG antibody, additional serum samples may be utilized to monitor for potential daratumumab interference with the IFE.

Time to response, DoR, TTP, and PFS will be calculated based on the investigator's response assessment. Subjects also will be followed for OS. All time-to-event endpoints will be estimated from the time of study enrollment, except DoR which will be estimated at the time from response.

- Myeloma paraprotein
- Serum immunoglobulins
- Serum Free Light Chain
- Serum beta-2 Microglobulin
- Bone marrow aspiration/biopsy
- Radiographic assessments of lytic bone lesions
- Extramedullary plasmacytoma (EMP) assessments
- Radiographic assessments of lytic bone lesions (skeletal survey)
- Eastern Cooperative Oncology Group (ECOG) performance status
- Quality of Life (QoL) as measured by the descriptive system of the EQ-5D questionnaire (subjects enrolled in Cohort B only)

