### ***Overall Survival and Subsequent Anti-MM Therapies***

During the follow-up period, survival status and subsequent therapies for MM must be collected and entered into the eCRF. All subjects will be assessed 4 times a year (every 3 months) to determine survival status for up to 5 years after the last subject is enrolled in each respective cohort. Primary cause of death (medical condition) is to be recorded in the eCRF and the subject's medical record. All subsequent therapies given for MM must be collected and entered into the eCRF.

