#### **Duration of Response**

Duration of response, calculated for responders only, is defined as time from the initial documented response (PR or better) to the first confirmed PD or until death from any cause. Subjects without documented progression will be censored at the time of their last response assessment.

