#### **Overall Survival**

Overall survival will be calculated as the time from start of treatment until the time of death from any cause. If no death is recorded the subject will be censored at the time the subject was last known to be alive.

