### **Deaths**

Deaths during treatment (defined as deaths from the first dose and within 28 days after the last dose of study medication) and during the long-term follow-up phase shall be summarized by frequency of occurrence and corresponding percentage by cause of death per period (during treatment or follow-up) as well as overall.

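### The PFS rule counts only on-treatment deaths, contradicts itself on censoring and has two time origins; the size and direction of any bias cannot be settled from the documents

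*Combined protocol and SAP*

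**What the plan says.** Section 10.6, Progression-free Survival, measures from the start of treatment to investigator-determined PD "or death from any cause on study treatment, whichever comes first". It then says: "Subjects not experiencing a documented progression will be censored at the time of their last response assessment". If there was no assessment, censoring is at trial enrollment.

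The neighbouring definitions differ:

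- **TTP:** "Time to progression will be calculated as the time from start of treatment until PD". It has no death component, and its censoring sentence is the same as the one for PFS.
- **DoR:** runs from first response "to the first confirmed PD or until death from any cause". There is no on-treatment limit, but subjects without documented progression are again censored at the last response assessment.
- **OS:** "Overall survival will be calculated as the time from start of treatment until the time of death from any cause".

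The Protocol Summary, Overview of Efficacy Assessments, states: "All time-to-event endpoints will be estimated from the time of study enrollment", with DoR as the only exception. Section 10.6 uses the start of treatment for TTR, TTP, PFS and OS.

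Deaths after treatment are collected. Section 6 states: "All subjects will be assessed 4 times a year (every 3 months) to determine survival status", for up to 5 years after the last enrollment in the cohort. Response is assessed on Day 1 of each cycle and at the discontinuation visit. Table 1 schedules no response assessment after that.

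**The concern.** Treatment can end without PD, for example through toxicity or withdrawal. A subject who leaves for these reasons and then dies has met the usual meaning of a PFS event, yet the rule censors that subject at the last assessment. If those who stop early are frailer, the censoring is informative and the Kaplan-Meier estimate no longer describes the enrolled population.

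The second problem is ambiguity. Two programmers working from the same data could produce different PFS curves, depending on which of the two sentences they follow and which origin they use. PFS is to be reported in both the ITT and EE sets and updated at the end of follow-up, so the ambiguity would carry through every report.

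**Working it through.** The plan states no PFS median, event count or power, so there is no figure of its own to reproduce. The first two steps need only the text. The third is illustrative.

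**1. Events and censoring side by side (subjects with no documented PD who die)**

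| Subject | PFS event sentence | PFS censoring sentence | DoR event sentence (responders) | DoR censoring sentence | OS |
|---|---|---|---|---|---|
| Dies on treatment | event | censored | event | censored | event |
| Stops, then dies | not an event | censored | event | censored | event |

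The first row is a contradiction within PFS. The second is a loss of recorded deaths. DoR has no on-treatment limit but shares the faulty censoring sentence. The PFS text does not define being on study treatment. The only window for deaths is in the safety section on deaths, "defined as deaths from the first dose and within 28 days after the last dose of study medication", and it is not linked to PFS.

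**2. Time origin**

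- Treated subject with no assessment: time = enrollment date minus treatment start date, which is zero or negative.
- Never-treated subject, who belongs to the ITT set by Section 10.2: there is no treatment start date, so the time is undefined.
- With enrollment as origin, both have time zero if alive.

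**3. How far the on-treatment limit could move the median**

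All inputs are assumptions. Let m be the median time to PD, p the share who stop without PD, and h the median time from stopping to death. Set the on-treatment death hazard at 10% of the PD hazard. Assume exponential times and that PD after stopping is not observed.

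- λ = ln 2/m; a = 1.1λ; stopping hazard d = a·p/(1−p); μ = ln 2/h.
- On-treatment rule: median = ln 2/a = m/1.1.
- Literal censoring sentence (PD only): median = m.
- All deaths counted: solve S(t) = 0.5, where S(t) = exp(−(a+d)t) + d·[exp(−μt) − exp(−(a+d)t)]/(a+d−μ).

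Check at m = 20, p = 20%, h = 6: a = 0.03812, d = 0.00953, μ = 0.11552. At t = 16.44, S = 0.4569 + 0.0431 = 0.500.

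The 7% and 12% stopping shares are the AE discontinuation rates quoted in Section 1.2 for the earlier phase 2 study (POM+LD-dex and POM alone). The 4.6- and 6.3-month values are PFS medians quoted in Section 1.2 for POM+LD-dex, used here as stand-ins for m. The populations there were heavily pretreated.

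| m (months) | p | h (months) | On-treatment rule | All deaths | Difference |
|---|---|---|---|---|---|
| 20 | 7% | 6 | 18.18 | 17.59 | +0.59 |
| 20 | 12% | 6 | 18.18 | 17.15 | +1.03 |
| 20 | 20% | 6 | 18.18 | 16.44 | +1.74 |
| 20 | 35% | 6 | 18.18 | 15.03 | +3.15 |
| 20 | 20% | 18 | 18.18 | 18.17 | +0.01 |
| 6.3 | 20% | 6 | 5.73 | 5.75 | −0.02 |
| 6.3 | 20% | 12 | 5.73 | 6.03 | −0.30 |
| 4.6 | 20% | 6 | 4.18 | 4.30 | −0.12 |
| 4.6 | 20% | 12 | 4.18 | 4.48 | −0.30 |

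The reversal has a simple cause. When unseen PD would have come sooner than death, counting a late death as the event lengthens PFS.

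A second model lets PD after stopping be observed in the all-deaths comparator. It was simulated with 200,000 subjects per scenario, a 36-month cut-off and monthly hazards of 0.004–0.01 for on-treatment death, 0.01–0.02 for stopping and 0.05–0.15 for off-treatment death. The on-treatment rule was then higher throughout. At a 6-month PD median the gap ran from 0.04 months (5.54 vs 5.50) to 0.28 (5.79 vs 5.51). At 18 months it ran from 0.63 (14.34 vs 13.71) to 3.23 (16.17 vs 12.94).

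**The case against.** The strongest reply is that little depends on this. ORR is the primary endpoint. PFS is a Kaplan-Meier median with a confidence interval, without a test. Deaths after PD are already PFS events, and every death remains in OS. This stands, and it limits the severity.

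A reader might infer that PFS will be overstated. The documents do not support that as a fact. They give no rate of stopping without PD and no survival after stopping in this trial, and the table shows both signs under plausible inputs. The larger gaps need slow progression, substantial stopping and early death together.

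A reader might also infer that the plan means to drop all deaths. The event sentence expressly includes on-treatment deaths, so the censoring sentence is better read as a drafting contradiction than as intent. For the same reason, the contrast between PFS and DoR should not be pressed too far. It exists in the event definitions, but on a literal reading DoR loses its deaths as well.

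It is also tempting to say that the result would compare unfairly with published PFS. The documents do not give the PFS definitions of the studies they cite, so that argument is not available.

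Finally, simply counting every death is incomplete. New anti-myeloma therapy may begin after intolerance, and no response assessment is scheduled after discontinuation. A death long afterwards could stand in for a much earlier, unseen progression. This objection stands and shapes the fix.

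**Conclusion.** Wrong as written; should be fixed. Three defects rest on the text alone: the on-treatment limit on deaths, the censoring sentence that contradicts it (and recurs in DoR), and the conflict between enrollment and start of treatment as origin. Nothing elsewhere in the documents repairs them.

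The consequence is an ambiguous PFS subject to informative censoring. The likely bias is upward when PD is slow and death soon follows stopping: about 0.6 to 3 months for 7% to 35% stopping, a 20-month PD median and 6 months from stopping to death. It is near zero or reversed at PD medians of about 5 to 6 months when later PD goes unobserved, and near zero at 20 months when deaths after stopping are slow (18-month median). These sizes rest wholly on assumed rates.

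**What to change.** Amend Section 10.6 and align the Protocol Summary:

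- Define PFS as time to first PD or death from any cause, whether on or off study treatment.
- Censor at the last response assessment only subjects who are alive without PD. Use the same censoring wording for DoR.
- Use the date of enrollment, as in the Protocol Summary, as the single origin for PFS, TTP, OS and TTR in the ITT set. DoR continues to run from first response.
- For PFS, censor subjects with no post-baseline assessment at the enrollment date (time zero) unless they died. Cycle 1 Day 1 would not serve, because never-treated subjects have none.
- Add a sensitivity analysis that censors at the last assessment before new anti-myeloma therapy or before a long unassessed interval, with the interval's length fixed in advance.

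The cost is revised wording and a small amount of extra analysis. Death dates are already collected every 3 months, so no new data are needed. The sponsor should accept that the PFS estimate may move in either direction.

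### PFS counts only on-treatment deaths, with that limit undefined, while duration of response counts any death, so the same known death is an event for one endpoint and a censoring for the other

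*Combined protocol and SAP*

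**What the plan says.** All three definitions stand in Section 10.6 under Secondary Efficacy Endpoints.

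- **PFS.** "Progression-free survival will be calculated as the time from start of treatment until the time of PD" or "death from any cause on study treatment, whichever comes first". Then: "Subjects not experiencing a documented progression will be censored at the time of their last response assessment", or at enrolment if there was no assessment.
- **DoR.** From first documented response "to the first confirmed PD or until death from any cause". Then: "Subjects without documented progression will be censored at the time of their last response assessment".
- **OS.** "Overall survival will be calculated as the time from start of treatment until the time of death from any cause", with no on-treatment limit.

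The PFS definition does not say when on-treatment status ends. The nearest definitions are in Section 10.7. The Deaths paragraph treats as deaths during treatment "deaths from the first dose and within 28 days after the last dose of study medication", and the Adverse Events paragraph gives the treatment phase the same 28-day tail. Section 10.6 refers to neither.

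Section 6 (Assessment of Response) and Table 1 schedule response assessments on Day 1 of each cycle and at the discontinuation visit, and none after that. Section 6 also has survival status collected every 3 months for up to 5 years after the last enrolment in the cohort. Subjects may stop for toxicity or withdrawal without progression (Section 4.1).

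**The concern.** Two secondary endpoints built from the same two events, progression and death, use different death rules, and no reason is given. A subject who stops without progression and later dies is known to the study to have died. PFS discards that death and DoR keeps it.

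Three things are at stake. Deaths soon after stopping for toxicity or decline are unlikely to be independent of prognosis, so censoring those subjects at their last assessment is informative. Because the on-treatment limit is undefined, two programmers can produce two PFS datasets from the same records. And Section 10.6 has PFS and DoR updated at the end of long-term follow-up, when most post-treatment deaths will have accumulated.

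**Working it through.** The plan states no sample size, event count or target for PFS or DoR, so there is no figure to reproduce. The check applies the written rules to individual subjects.

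**Within-subject rule.** Let R = first response, L = last response assessment (here also the last dose) and D = death, in days from start of treatment, with no progression and D after on-treatment status has ended.

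- Plan: PFS = L, censored. DoR = D − R, event.
- So DoR > PFS exactly when D − R > L, that is, when D − L > R. The gap from last assessment to death must be longer than the time to response.
- With one death rule: PFS = D and DoR = D − R. Then PFS − DoR = R, so DoR can never exceed PFS.

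| R | L | D | PFS, limit ends at last dose | PFS, limit ends 28 days later | DoR |
|---|---|---|---|---|---|
| 56 | 140 | 230 | 140 censored | 140 censored | 230 − 56 = 174 event |
| 28 | 140 | 169 | 140 censored | 140 censored | 169 − 28 = 141 event |
| 28 | 140 | 160 | 140 censored | 160 event | 160 − 28 = 132 event |

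In row 1 DoR exceeds PFS by 174 − 140 = 34 days on either reading. With one death rule that subject has PFS 230 and DoR 174. In row 3 DoR does not exceed PFS, but the PFS record depends on which limit is assumed.

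**Censoring sentences.** Both depend only on whether progression was documented. Taken literally, a subject who dies without progression is censored, which voids the death event defined in the sentence before. The first response assessment is at Cycle 2 Day 1 (Table 1 footnotes), so on that reading a death before it would be a PFS censoring at enrolment.

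**Size for PFS, by simulation under assumed rates (not from the documents).** Exponential progression on treatment with median 10 months; on-treatment death 0.5% per month; stopping without progression 1.5% or 3% per month (17% or 29% of subjects); 10% of those who stop die within 2 months, spread evenly, and the rest die at 2% or 5% per month. Kaplan-Meier estimates:

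- Plan rule, limit at last dose: 12-month PFS 41%, median about 9.3 months.
- Deaths within 84 days of stopping counted: 38 to 40%, median 8.7 to 9.1 months.
- The difference is about 1 to 2 points in three of the four settings and just under 3 in the heaviest. If the 28-day window is borrowed, roughly half of it remains.

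**Direction for DoR, same assumed subjects, time counted from start of treatment.** Subjects who stopped and are alive at the data cut are censored back at their last assessment, as the plan says. The PFS death rule gives 17% event-free at 24 months. The DoR death rule gives 13 to 16% with 12 to 36 months of follow-up and about 18 to 22% with 60 to 80 months. With short follow-up the observed deaths count while survivors are pulled back. With long follow-up most stoppers are carried to a late death.

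**Counting every later death in PFS.** A second set of assumptions (median time on treatment 10 months, 20% stopping without progression, 60 months of follow-up) moves median PFS from 12.6 to 11.8 months when median survival after stopping is 6 months, but from 12.5 to 12.8 months when it is 24 months.

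**The case against.** Much of the case against a stronger claim stands.

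- A reader might infer that any death just after stopping is lost, for example one 10 days after the last dose. That holds only if on-treatment status ends with the last dose. Section 10.7 describes "Deaths during treatment (defined as deaths from the first dose and within 28 days after the last dose of study medication", and with that window the death is a PFS event. What is established is that the term is undefined for PFS and that later deaths are lost on either reading.
- A reader might infer that PFS and DoR curves which cross or disagree show the error. They do not. PFS covers all subjects and DoR only responders. The protocol's own background has median DoR above median PFS (7.7 versus 4.6 months for POM+LD-dex in phase 2 of CC-4047-MM-002; 11.4 versus 6.3 months in the cyclic arm of the IFM study). Only the within-subject anomaly is evidence.
- A reader might infer that DoR is always biased upward. The calculation shows the direction reversing with follow-up.
- The literal reading of the censoring sentences cannot be used together with the DoR example, because it would remove the DoR death as well. The amendment history records that the death clause was added to DoR, so the intent is clear and the sentence is loose drafting.
- Progression dates are collected with subsequent regimens in follow-up, and new therapy should wait for progression or intolerance. Carrying a responder through later treatment lines is therefore a worst case, although the plan does not say that those dates feed DoR.
- Both endpoints are secondary, descriptive, single-arm Kaplan-Meier summaries without a test.

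None of this reconciles the two death rules, and no other section does.

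**Conclusion.** The inconsistency is real and follows from the text without any assumed rate. Known deaths after treatment ends without progression are DoR events and PFS censorings. DoR exceeds the same subject's PFS whenever the gap from last assessment to death is longer than the time to response. The undefined on-treatment limit and the two censoring sentences leave the programming open to more than one result.

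The size is not fixed by the documents. Omitting deaths soon after stopping makes PFS modestly too favourable under the assumed rates, about 1 to 2 points at 12 months. No direction can be claimed for DoR without stating the follow-up, nor for PFS once deaths long after stopping are counted. This should be corrected before the secondary analyses. It does not touch the primary ORR analysis or the sample size.

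**What to change.** In Section 10.6:

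1. Delete the on-treatment qualifier from the PFS death clause.
2. Define the event for both PFS and DoR as the first of progression or death from any cause. Only the time origin then differs.
3. Change both censoring sentences so that they apply to subjects who have neither progressed nor died.
4. State one rule, applied to both endpoints, for subjects who start new anti-myeloma therapy without progression: either censor at the last response assessment before the new therapy or follow regardless of it. Report the alternative as a sensitivity analysis. This also shows how far deaths long after stopping drive the result.

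Do not add a rule that censors deaths after two or more missed assessments once treatment has been discontinued. No response assessments are scheduled then, so the rule either has no meaning or censors again many of the deaths that step 1 restores.

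The cost is amended wording and minor programming. Death dates, response assessments and start dates of subsequent therapy are already collected. Reported PFS may be slightly shorter where early post-treatment deaths dominate.

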#### **Overall Survival**

Overall survival will be calculated as the time from start of treatment until the time of death from any cause. If no death is recorded the subject will be censored at the time the subject was last known to be alive.

## **Quality of Life (QoL)**

Using EQ-5D scoring instructions, overall scores will be analyzed for subjects enrolled in Cohort B using change from the screening assessment at each post-screening time point. The worst change from baseline among all available post-baseline measurements for each subject will also be analyzed. Change scores from baselines will be analyzed using mixed model using baseline covariates as adjustment.

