**Table 1: Table of Events (Continued)**

Procedures	Screening (Days -28 to 0)	Day 1 (± 3 days) of Every 28-day Cycle	Cycle 1 & 2 Day 8 (± 3 days) Day 15 (± 3 days) Day 22 (± 3 days)	Cycle 3, 4, 5, 6 Day 15 (± 3 days)	Treatment Discontinuation on Visit (± 3 days)	Follow-up Visit (Within 28 Days Post Treatment Discontinuation) (± 3 days)	Long-term Follow-up Every 3 Months (84 ± 14 days) for Up to 5 Years After Last Subject Enrollment in each respective cohort
Other Assessments							
Exploratory biomarker sampling: whole blood (at selected sites) t	X	X t	X t	-	X t	-	-
Exploratory biomarker sampling: bone marrow aspirate (at selected sites) t	X	-	-	-	X	-	-
Exploratory biomarker sampling: normal tissue (saliva samples) at selected sites u	X	-	-	-	-	-	-
EQ-5D (for subjects enrolling in Cohort B) v	X	X v	-	-	X	-	-
Investigational Product Dispensation							
Oral POM dispensation/ accountability	-	X	-	-	X	-	-
Oral dex dispensation/ accountability	-	X	-	-	X	-	-
DARA intravenous dispensation/infusion/ accountability	-	X	X	X	X	-	-

ANC = absolute neutrophil count; ALC = absolute lymphocyte count; ALT = alanine aminotransferase; AST = aspartate aminotransferase; BUN = blood urea nitrogen; CR = complete response; CT = computed tomography; dex = dexamethasone; ECG = electrocardiogram; ECOG = Eastern Cooperative Oncology Group; eCRF = electronic case report forms; FCBP = females of childbearing potential; GGT = gamma glutamyl transferase; HGB = Hemoglobin; HCT = Hematocrit; IAT = indirect antiglobulin test; ICD = Informed Consent Document; LD = low-dose; LDH = lactate dehydrogenase; MCV = mean corpuscular volume; MM = multiple myeloma; MRI = magnetic resonance imaging; PD = progressive disease; POM = Pomalidomide; PR = partial response; RBC = red blood cell; SAE = serious adverse event; SGOT = serum glutamic oxaloacetic transaminase; SGPT = serum glutamic pyruvic transaminase; SPM = second primary malignancy; VTE = venous thromboembolism; WBC = white blood cell.

a Results for any local cytogenetic testing, if available as part of medical history, will be collected in the electronic case report forms (eCRFs).

b Date of initial diagnosis and myeloma stage per the International Staging System and/or the Durie-Salmon Staging System ([Appendix H](#)) at initial diagnosis (if available) will be collected as part of the disease diagnosis assessment.

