  - p Assessment/measurement at specified time-points only required if EMPs are present. If EMPs are clinically assessable, clinical assessment will be performed at screening, at every Cycle Day 1, and at treatment discontinuation. If EMPs are only assessable radiographically (x-ray and/or conventional [spiral] CT/MRI scan), scans are required at screening, at Cycle 3 Day 1, every 3 cycles thereafter (Cycle 6 Day 1, Cycle 9 Day 1, etc.) during treatment, at treatment discontinuation, and when clinically indicated to confirm response ( $\geq$  PR).
  - q A skeletal survey by x-ray will be performed at screening and when clinically indicated per the investigator's discretion. If a skeletal survey was performed within 60 days prior to the start of Cycle 1, it may be used for the screening assessment if approved by sponsor. Refer to [Appendix C](#) for detailed requirements.
  - r Response, including PD, will be assessed by investigators using the modified International Myeloma Working Group criteria ([Appendix B](#)). Response assessment should also be repeated at the time of response ( $\geq$  PR) or PD confirmation. The first response assessment will occur at Day 1 of Cycle 2.
  - s Subsequent anti-myeloma regimens: type of treatment, start and stop dates, date of progression and best response whenever possible.
  - t For Cohort A and Cohort B subjects who consent to participate in biomarker analysis may undergo collection of bone marrow aspirate and whole blood samples at screening, response assessment (confirm CR) and disease progression, and when clinically indicated. Additionally, whole blood samples will be collected at Day 1 of Cycle 3,5 and

treatment discontinuation for Cohort A and **C1D1, C1D8, C1D15, C2D1, C2D15, C3D1, C5D1 and treatment discontinuation** for Cohort B. For Cohort C, all subjects will provide bone marrow aspirate at screening and treatment discontinuation.

u For Cohort A and Cohort B subjects who consent to participate in biomarker analysis may undergo collection of normal tissue (which may include saliva samples) at screening only.

v For subjects enrolled in Cohort B, Quality of Life (QoL) measured with the descriptive system of the EQ-5D will be provided to each subject to complete on Day 1 of every cycle prior to any study treatment (POM, DARA, LD-dex) administration and at treatment discontinuation.

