## 6. PROCEDURES

### Study Entry

Prior to screening, subjects must sign an informed consent document. All screening assessments must be completed within 28 days prior to start of Cycle 1, with the exception of the skeletal survey, which may be performed within 60 days prior to initiation of study treatment, with the approval of sponsor.

Confirmation of diagnosis (including date of confirmed initial diagnosis and, if available, myeloma stage at time of initial diagnosis per the Salmon-Durie Criteria and/or the International Staging System [[Appendix H](#)]), medical history, prior cancer and surgical history, and review of prior medications should be documented during the screening period. All prior radiotherapy, surgeries, and anti-myeloma therapies must be recorded in the electronic case report form (eCRF), including approximate dates for each therapy and the date of progression for each regimen. Results for any local cytogenetic testing (prefer fluorescence in situ *hybridization* [FISH] results), if available, as part of medical history, will be collected in the eCRF. See [Table 1](#) (Table of Events) for a complete list of the required assessments during screening.

If the subject's safety and efficacy laboratory assessments performed at screening are within 7 days of enrollment into the study, they do not need to be repeated at Cycle 1 Day 1 and can be used as baseline results. The start of study drug dosing is designated as Cycle 1 Day 1. A 14-day wash-out period is required for any prior anti-myeloma therapy before study treatment is initiated.

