### ***Quality of Life (QoL)***

For subjects enrolled in Cohort B, Quality of Life (QoL) as measured by the descriptive system of the EQ-5D will be provided to each subject to complete on Day 1 of every cycle prior to any study treatment (POM, DARA, LD-Dex) administration and at treatment discontinuation. See [Appendix I](#) for EQ-5D questionnaire to be used.

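### EQ-5D change in Cohort B is taken from screening with no separate definition of baseline, so the untreated Cycle 1 Day 1 form can count as post-baseline and even as the worst change

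*Combined protocol and SAP*

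**What the plan says.** The Quality of Life paragraph of Section 10.6 gives three analyses of the EQ-5D overall score in Cohort B:

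- By visit: scores are analysed "using change from the screening assessment at each post-screening time point".
- Worst value: "The worst change from baseline among all available post-baseline measurements for each subject will also be analyzed".
- Model: "Change scores from baselines will be analyzed using mixed model using baseline covariates as adjustment".

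The first names screening as the reference. The other two use the word baseline. The paragraph neither says that baseline means screening nor gives another definition.

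On timing, the Quality of Life paragraph of Section 6 gives subjects the form "to complete on Day 1 of every cycle prior to any study treatment (POM, DARA, LD-Dex) administration and at treatment discontinuation". Footnote v of Table 1 says the same. The EQ-5D row of Table 1 itself marks screening as well as Day 1 of each cycle and treatment discontinuation. Section 6, Study Entry, allows screening assessments up to 28 days before Cycle 1 and refers to Table 1 "for a complete list of the required assessments during screening". Section 3.3 lists quality of life as an exploratory endpoint for Cohort B only.

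**The concern.** Day 1 of every cycle includes Cycle 1, so each Cohort B subject is scheduled to complete two forms before any drug: one at screening and one on Cycle 1 Day 1. If screening is the reference and everything later is post-baseline, the second untreated form becomes an on-study observation.

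This matters for two reasons. First, there is reason to expect change between the two forms. Subjects must have documented progression (Section 7.2, criterion 4) and a 14-day wash-out of prior anti-myeloma therapy (Section 6, Study Entry), and screening may precede or overlap that wash-out. Second, Cohort B is open-label and evaluated separately from the other cohorts (Section 10.1), so no control group is available against which to set off pre-treatment drift.

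The protocol is more careful elsewhere. Screening laboratory values can stand in for Cycle 1 Day 1 only if taken within 7 days of enrollment (Section 6, Study Entry). Treatment-emergent adverse events are judged against the pre-treatment state, with the treatment phase starting at first dose (Section 10.7). EQ-5D has neither safeguard, although a pre-dose form on the day of first dosing is already scheduled.

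**Working it through.** **No figure to reproduce.** The documents give no EQ-5D sample size, SD, margin or completion count. The check is therefore a reading of the text, followed by an illustration on stated assumptions.

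**Step 1: the passages side by side.**

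| Form | Table 1 row | Section 6 text and footnote v | Before first dose? | Status under Section 10.6 |
|---|---|---|---|---|
| Screening | Scheduled | Not mentioned | Yes | Reference value |
| Cycle 1 Day 1 | Scheduled | Scheduled, pre-dose | Yes | Post-screening, so a change score |
| Day 1 of later cycles | Scheduled | Scheduled | No | Change score |
| Discontinuation | Scheduled | Scheduled | No | Change score |

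The second row is the problem. The step from post-screening to post-baseline is the natural reading, since screening is the only reference the paragraph names, but it is not an explicit definition.

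**Step 2: effect on change by visit.** Write S for the screening score, C for Cycle 1 Day 1 and Y for any later score. Then

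Y − S = (Y − C) + (C − S).

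The term (C − S) arises entirely before treatment and is carried into every later change from screening. If its mean is d, every later by-visit mean shifts by d. The documents give no value for d.

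**Step 3: effect on the worst change.** The worst change is a minimum, so one more value can only leave it unchanged or make it worse. To size this, 200,000 subjects were simulated with no true change over time. Each score is a subject effect with variance ρ plus independent error with variance 1 − ρ, so the SD of a single score is 1. Lower is taken as worse. K is the number of on-treatment forms. The values ρ = 0.5 and 0.7 and K = 1 to 12 are assumptions.

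- Counted: mean of min(C, on-treatment scores) − S.
- Not counted: mean of min(on-treatment scores) − S.

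| ρ | K | Counted | Not counted | Difference |
|---|---|---|---|---|
| 0.5 | 1 | −0.396 | 0.004 | −0.400 |
| 0.5 | 3 | −0.731 | −0.600 | −0.131 |
| 0.5 | 6 | −0.955 | −0.894 | −0.061 |
| 0.5 | 12 | −1.178 | −1.151 | −0.027 |
| 0.7 | 1 | −0.307 | 0.002 | −0.309 |
| 0.7 | 3 | −0.563 | −0.463 | −0.100 |
| 0.7 | 6 | −0.742 | −0.695 | −0.047 |
| 0.7 | 12 | −0.913 | −0.892 | −0.021 |

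With no true change, the Cycle 1 Day 1 form is as likely as any on-treatment form to be the lowest, so its share is 1/(K + 1): 1/2 = 50%, 1/4 = 25%, 1/7 = 14% and 1/13 = 8%. The simulation gave 50%, 25%, 14% and 8%.

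The third column is well below zero from K = 3 onward. Most of the apparent worsening there comes from taking a minimum, whichever rule is used. Only the last column belongs to this point.

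**Step 4: the limiting case.** A subject with only a screening and a Cycle 1 Day 1 form would have a worst change made up wholly of pre-treatment change.

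**The case against.** The strongest reply is that the paragraph leaves baseline undefined rather than fixing a wrong one, and that a change reported by visit labels Cycle 1 Day 1 plainly enough for nobody to read it as a drug effect. The first half is fair: equating baseline with screening is an inference. The second holds for that one visit only. The worst-change summary carries no visit label, and Step 2 shows that later visits still carry the pre-treatment drift.

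A second reply is that removing Cycle 1 Day 1 from the post-baseline values would be enough. In the simulation, using Cycle 1 Day 1 as the reference does give practically the same means as leaving it out. But the simulation assumes no drift. If d is not zero, a screening reference still passes it on to every later visit.

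A third reply is that the effect is small and nothing depends on it. That largely stands: the endpoint is exploratory, untested and unpowered, and with many on-treatment forms the artefact is negligible.

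A fourth reply is that a separate analysis plan, which Section 4.4 mentions, may define the baseline. No such definition appears in the document available. If one exists and uses the last pre-dose value, only the schedule wording remains to be aligned.

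A reader might go further in two ways that the documents do not support:

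- That a site following Section 6 would collect no screening EQ-5D. Table 1 schedules one, and Section 6, Study Entry, sends sites to Table 1 for the screening list. The omission from the Section 6 text and footnote v is an inconsistency, not an absent assessment.
- That all 112 Cohort B subjects are affected, or that subjects drop out of the analysis for want of a screening form. There are no EQ-5D completion counts, and Section 10.2 allows for enrolled subjects who were never dosed. The schedule shows what should be collected, not what was.

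**Conclusion.** The point holds as a minor one. On the natural reading of Section 10.6, an untreated Cycle 1 Day 1 score enters the change analyses and can be a subject's worst change, in a cohort without a control arm. On the assumptions above, the extra apparent worsening in the worst-change mean is about 0.3 to 0.4 SD for subjects with one on-treatment form, 0.10 to 0.13 SD with three, and 0.02 to 0.03 SD with twelve. It therefore falls mainly on subjects who leave treatment early. The shift in by-visit change equals the mean pre-treatment drift, which is unknown.

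This rests on reading baseline as screening and, for the figures, on the assumed correlations, equal variances and no true change. Overall response rate, the secondary endpoints, sample size and power are untouched.

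**What to change.** In Section 10.6, define EQ-5D baseline as the last assessment before the first dose: the Cycle 1 Day 1 form, or the screening form if that one is missing. State that only values after the first dose are post-baseline, and apply this to the by-visit change, the worst change and the mixed model alike. Change from screening can be kept as a sensitivity summary if wanted.

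Separately, add screening to the EQ-5D timing in the Section 6 Quality of Life paragraph and in footnote v, so that both match the Table 1 row.

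The cost is a sentence or two in the analysis section and two wording corrections in the schedule. No new data are needed, because both pre-dose forms are already scheduled.
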